### **Purpose**

The purpose of the research is to study a new safety monitoring system developed by SafelyYou to help care for a loved one with dementia. The goal is to provide better support for unwitnessed falls.

The SafelyYou Guardian system is based on AI-enabled cameras which detect fall related events and upload video only when these events are detected. The addition of a Human in the Loop (HIL) will alert the facility staff when an event is detected by the system. This would allow the facility to continue with its current safety precaution but add another level of support by using HIL's to monitor for falls in real-time and 24/7.

This process enables staff to know about falls without requiring residents wear a device and to see how falls occur for residents that cannot advocate for themselves while still protecting

Revision Date: 10/23/19

resident privacy by only uploading video when safety critical events are detected. Seeing how the resident went to the ground (1) prevents the need for emergency room visits when residents intentionally moved to the ground without risk and (2) allows the care team to determine what caused an event like a fall and what changes can be made to reduce risk.

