## **AIMS & HYPOTHESES FOR RANDOMIZED, WAITLIST-CONTROL STUDY.**

**Aim #1. To assess whether SafelyYou Guardian + HIL will lower fall rates.** Hypothesis 1. Compared to standard-of-care (waitlist control group), SafelyYou Guardian will reduce fall rates in study participant over the study period of 6 months.

**Aim #2. To assess how use of the SafelyYou Guardian affects time spent on the ground after a fall.** Longer time to fall discovery is associated with higher human suffering and often leads to higher medical morbidity/mortality. Hypothesis 2: SafelyYou Guardian + HIL will reduce time to fall discovery (time from fall to staff notification) to under 5 minutes and reduce time spent on the ground to under 15 minutes. Since there is no way to measure control participants time spend on the ground, the aim will not have a comparison but will be descriptive.

**Aim #3. To assess whether SafelyYou Guardian will lead to improvement in hard clinical outcomes.** Hypothesis 3: SafelyYou Guardian participants will lower ED visits and hospitalizations when compared to control. This reduction in ED and hospitalization will correlate with reduced fall rates (aim #1) and reduced time spent on the ground (aim #2). We will review the strength of the association with aim #1 and #2 outcomes.

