### Design

For Aim 1, we plan to recruit 460 study participants from 19 memory care facilities. For the purpose of this study, facilities will include Skilled Nursing Facilities (SNFs), or equivalent. Aim 1 will be a randomized controlled study using a waitlist control group. The randomization will occur at the individual (resident) level within each facility to control for variations at each facility in terms of facility size, facility administration, and staff training. During the first 6 months, n=230 will receive the intervention (SafelyYou Guardian, i.e. real-time alarms through a phone call from the HIL to the facility, front line staff intervention, and OT review), and n=230 will not receive the intervention. This design is the most rigorous way to test the intervention against the control: the randomization allows for control of confounding variables and has been previously used in the evaluation of medications, non-pharmacological, and mobile electronic interventions (where use of placebo treatment and blinding is not feasible) [87-89]. Previous work used a baseline as control, allowing possible confounding variables. As we recognize that 50% of the interested participants will not receive the intervention, those residents will be offered the intervention for a 6-month extension period (in order to accomplish Aim 2). This is the best compromise between the need for a rigorous randomized controlled trial vs. ethical responsibility to maximize benefit to each study participant.

For Aim #2, we will measure response times to each fall and the amount of time a resident spends on the ground after each fall. We intend to include all 460 participants' data from Aim #1. These will be participants who receive the initial intervention (n=230) and the additional participants who are on the waitlist control group who will receive the intervention in the second 6month period. The design for Aim #2 is observational in nature. The significance is that a large cohort of video data about the naturalistic progression of falls in residents with dementia has never been conducted to our knowledge. We will determine if the two time variables (time to fall discovery by staff and time spent on the ground after a fall, controlling

for baseline participant characteristics – i.e., demographics and medical conditions) and facility size, will predict need for ER visits or hospitalizations.

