Event Detection: As videos are recorded at the facility, the computer located in the facility will analyze the video streams and keep a buffer of 10 minutes of prior video from each camera. If a resident is detected on the ground or a resident is detected going from a laying position to a sitting position in bed, an alert will automatically be sent to the Magellan team, and the 10-minute buffer video will be uploaded. They will confirm a resident is on the ground by viewing a blurred version of the video as described above and reach out to the facility staff by phone or e-call system to inform them of the situation. The 10 minutes of video after a resident on the ground is confirmed will also be uploaded, enabling 20-minute window into how the fall occurred with minimal burden on the frontline care team. As long as an event such as a resident on the ground is detected, the system will continue to upload video in this way.

Abuse Reporting: Abuse reporting will be conducted following the requirements of the Welfare and Institutions (WIC) code. If any potential evidence of abuse is discovered, facility management will be immediately alerted. Note that evidence of abuse may be missed by the SafelyYou system since only video of detected events is uploaded. The SafelyYou system is not meant to be a system for reporting abuse; it is meant to be a system for improving fall prevention practices in memory care. The research system is not intended to screen for abuse or theft suspicions. As discussed below, only video of detected events are available. It is thus very possible that incidents of abuse or theft are never uploaded for viewing by facility personnel.

Confidentiality: Study data will be handled as confidentially as possible. If results of this study are published or presented, individual names and other personally identifiable

information will not be used unless you give explicit permission for this in the separate media release form.

To minimize the risks to confidentiality, we will do the following:

- During data collection, all data will be transmitted over a secure channel.
- Research records, including video recordings and computer-based data, will be stored in an encrypted format, on a password-protected computer in a physically secure room.

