#### Clinical outcomes.

For Aim #1, the primary outcomes are the number of falls detected by facilities using the adverse incident reporting system as per routine facility protocol. While use of video detected falls will be used in the intervention group to assist with prevention of future falls, we will not use this as the actual outcome measure: is not the standard-of-care, and the control group will not have video recorded outcomes. There is a bias for detecting falls using video since existing fall reporting systems do not capture falls which staff do not know about (e.g., when a resident is able to get back in bed after a fall). Staff-detected falls which automatically trigger adverse incident reporting is the “real-world” outcome measure and current stand-of-care. Thus, outcomes will differ by facility (each facility has different adverse incident reporting operations and implementation, hence the randomization at each facility will adjust for such variables).

Aim #2 will be a naturalistic observation of SafelyYou Guardian with HIL for 6 months. Specifically, for all the facilities, the use of the SafelyYou Guardian enables direct notification of falls to front-line staff in the facilities, by intervention of the HIL. We can directly measure time on the ground for the residents as follows: (1) The time of the fall is recorded by

SafelyYou Guardian (which detected it); (2) The time of intervention of the front-line staff is logged by the staff after finding the residents on the ground. This means that for the population with treatment, we can directly measure the time of fall discovery (successful call leading to front line staff intervention), and time on the ground (since time of the intervention is logged by the facility). This is because time on the ground for monitored residents can be measured precisely by video recording. Reduction of the time on the ground can be computed given the difference between the two.

Aim #3 will include number of ER visits and number of hospitalizations. We will obtain information about resident demographics, medical comorbidities, emergency room visits, and hospitalization data by asking the study participant legal representatives. In addition, we will have participant / participant Durable Power of Attorney complete HIPAA consent forms for release of medical records when indicated if the details of data are not available.

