Following the sample size for a time-averaged response methodology laid out in Fitzmaurice et al., we adjusted the total number of centers needed by a factor related to the number of observed months, anticipated participants per center (30% of 35 participants per center with 10% dropout) and the correlation between measurement months. The dropout rate was roughly at ~1% per month so a 10% dropout over 6 months is a conservative estimate. We assumed an extremely conservative estimate of the correlation between time points (months) of 0.8 and 6 months of follow-up. Reproducible R code is available at <https://github.com/[name]/>. We estimate that a total sample size of 460 ( $n=230/\text{arm}$ ) out of 19 facilities will be needed for a power of 80% to detect a 30% reduction in falls in the intervention group vs. control. Our approach of focusing on estimation and uncertainty and accepting the sample size collected for the main study, is congruent with experts' recommendations stating that the purpose of economic evaluation is not hypothesis testing; given there is no hypothesis testing, there is no requirement for a separate sample size calculation. For Aim 2, we will use similar descriptive statistics as described in Aim 1. For Aim 3, We will use a multivariate regression model to examine predictors of the main outcome, ER visits and hospitalizations (binary variable), using time to fall discovery by staff and time spent on the ground as the main predictors while controlling for baseline participant characteristics and facility characteristics.

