## **Risk/Benefit Assessment**

Minimal risk for study participants is expected as the system does not physically interact with study participants in any way and only provides supplementary support while all existing safety protocols in the facility remain in place.

Risks and/or discomforts include loss of privacy by placing a camera in the private room. Although the system is designed to keep video only when a fall is detected, false alarms do occur which can cause video to be uploaded at any time. If subjects feel uncomfortable about privacy once the cameras are installed, they may withdraw from the study at any time.

The research study personnel take several steps to protect the privacy of each participant. The recorded video does not have audio capability in order to protect private communication of residents and their visitors. Physical signs are posted visibly at the entrance to all private rooms containing cameras. The signs state that video recording is in progress to ensure all visitors and staff entering the room are aware of the camera. Cameras are placed in the private bedroom only, not in the private bathroom. Cameras record video only when an event is detected. Video (with no audio) will be reviewed by the research study personnel after collection. If more than one resident occupies a room, all roommates must provide informed consent for any to participate. All data is encrypted in transit and at rest.

Installation of the wall-mounted cameras will require inserting screws into the wall in the corner of the room adjacent to the ceiling and installing cabling which may be visible. No other risk of property damage is expected.

The ongoing safety procedures at the facility will remain in place.

The SafelyYou system has demonstrated reduced fall risk and unnecessary emergency room visits for those using it in previous studies with under 100 residents enrolled and hundreds more that have used it as a commercial product. We believe the system will provide significant benefits through faster response times to safety-critical situations, help staff make informed decisions about the need for transfer to the emergency room following unwitnessed falls, and reduce the overall frequency of falls through improved root cause analysis to minimize the risk of repeat falls, but this is active research, and we do not know if any of these benefits will occur for certain.

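### Aims 2 and 3 analyse discovery time and ground time without separating falls that staff witnessed from falls that nobody saw

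*Combined protocol and SAP*

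**What the plan says.** - **Goal (Purpose).** "The goal is to provide better support for unwitnessed falls".
- **Aim 2 scope (Design).** "we will measure response times to each fall and the amount of time a resident spends on the ground after each fall". No restriction by witness status follows.
- **Discovery time.** The Aims section sets the target as "time to fall discovery (time from fall to staff notification) to under 5 minutes". The Design section speaks of discovery by staff. Clinical outcomes says "we can directly measure the time of fall discovery (successful call leading to front line staff intervention", which ties the time to the reviewer's phone call.
- **Ground time (Clinical outcomes).** Measured from the video for monitored residents. The Aims section sets a 15-minute target and calls Aim 2 descriptive, without a comparator.
- **Aim 3 model (Data analysis paragraph).** A regression for a binary ER or hospitalization outcome, "using time to fall discovery by staff and time spent on the ground as the main predictors". The adjusters are the resident's baseline profile and the facility; nothing describes the fall itself.
- **ER decisions (Risk/Benefit Assessment).** The system is expected to "help staff make informed decisions about the need for transfer to the emergency room following unwitnessed falls".
- **What counts as a fall.** At the alert, human reviewers check position only: "They will confirm a resident is on the ground by viewing a blurred version of the video". The Purpose section treats intentional moves as a different kind of event, for which seeing the video "prevents the need for emergency room visits when residents intentionally moved to the ground without risk". For Aim 3, the Design section plans a follow-up case review of each detected fall. No section defines a fall or gives an exclusion rule.

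**The concern.** Hypothesis 2 is about what the system does for a resident whom nobody saw fall. If a caregiver is in the room, there is nothing to discover. Take a fall at 10:00 in front of staff, with the reviewer's call at 10:03. Discovery by staff takes 0 minutes, the call clock gives 3 minutes, and a call that led to staff intervention never happened, so there is no value. Two analysts could both follow the plan and report different results against the 5-minute target. With no comparator, nothing else in Aim 2 would reveal the difference.

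In Aim 3 witness status may act on both sides of the model. A witnessed fall is likely to have a shorter ground time and, under one reading, almost no discovery time. Staff also know how it happened, and the documents link the transfer decision to falls where they do not. Witness status belongs to the fall, so resident and facility covariates cannot remove it. A positive time coefficient could then mean only that unwitnessed falls are transferred more often.

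**Working it through.** The plan has no calculation on this point to reproduce: the 5- and 15-minute targets are thresholds, and the Aim 1 sample size is not affected. The documents give no witnessed share, time distribution or transfer rate by fall type. All three are assumed below, and the fall is taken as the unit of analysis.

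**1. Number of falls.** From the plan's monthly rate of 0.49 and its 30% reduction: 0.49 × 0.7 × 6 × 230 = 473 in one arm, and 0.49 × 0.7 × 6 × 460 = 947 over all residents. The main simulations use 450.

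**2. Aim 2, witnessed falls coded 0.** With witnessed share w and proportion p of unwitnessed falls found within 5 minutes, the pooled proportion is w + (1 − w)p.

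| w | p = 0.50 | Reported |
|---|---|---|
| 10% | 0.10 + 0.90 × 0.50 | 55% |
| 20% | 0.20 + 0.80 × 0.50 | 60% |
| 30% | 0.30 + 0.70 × 0.50 | 65% |
| 40% | 0.40 + 0.60 × 0.50 | 70% |

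If p = 0.337 (lognormal, median 7 minutes, log-SD 0.8), a 30% share reports 0.30 + 0.70 × 0.337 = 54%. Medians move too. With an unwitnessed median of 6 minutes and witnessed falls at 0.2 minutes, a 20% share gives a pooled median of 4.7 minutes, below the target although no unwitnessed fall was found sooner. With an unwitnessed median of 8 minutes, the pooled median is still 5.1 minutes at a 30% share.

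**3. Aim 3, discovery time, witnessed falls coded 0.** 1,000 data sets of 450 independent falls; unwitnessed discovery time lognormal with median 5 minutes and log-SD 0.8; transfer depends on witness status only, so time has no true effect. Logistic regression on discovery time, share of runs with p < 0.05:

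| w | Transfer 10% witnessed, 20% unwitnessed | Transfer 10% witnessed, 30% unwitnessed |
|---|---|---|
| 10% | 8% | 13% |
| 20% | 13% | 36% |
| 30% | 24% | 59% |
| 40% | 33% | 77% |

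The false odds ratio is 1.08 to 1.20 per 5 minutes at shares of 20–30%. Restricted to unwitnessed falls, rejection is 3–5%; with equal transfer rates it is 3–4%. In a separate run with 1,000 falls, log time, witnessed falls at 0.2 minutes and transfer 20% witnessed against 10% unwitnessed, the odds ratio per doubling is 0.86–0.87, so the bias can run either way.

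**4. Aim 3, discovery time, other codings.** Same settings, w from 20% to 40%, discovery time taken alone. Coded as a call time unrelated to witness status: rejection 4–5%. No value, so the fall drops out: 3–5%.

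**5. Aim 3, ground time.** Call-time coding for discovery, both times in the model, ground time assumed shorter for witnessed falls, 450 falls, w of 20–30%, transfer 10% against 20–30%, no true time effect. Ground time is falsely significant in 15–68% of runs, and in 4–7% once witness status is in the model. The range also depends on how much shorter witnessed ground times are, which the documents do not say.

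**The case against.** **Zero coding is not the plan's stated rule.** Clinical outcomes ties discovery to a call that brings staff in. Read literally, a fall in front of a caregiver has no discovery time and drops out, which is close to what the fix asks for. This stands for discovery time: steps 2 and 3 hold only under the zero reading, and step 4 shows no inflation under the other two. It does not clear Aim 3, because ground time comes from the video whichever clock is used for discovery and sits in the same model.

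**The analysis unit is a fall.** A reader might infer that every on-ground event, including a resident choosing to sit on the floor, is timed and analysed as a fall. The documents do not say this. The on-ground check is the alert step, the Design section says falls, and a case review is planned. What stands is narrower: without a definition or exclusion rule, it is unclear whether that review removes intentional moves.

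**The transfer gap is assumed.** All timed falls come from residents with cameras, and video is meant to show staff how an unseen fall happened. That could narrow the gap. Cameras are also in bedrooms only, so witnessed falls in shared areas are not timed, and the witnessed share may be at the low end of the range. Both points stand and reduce the likely size.

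**The aims are modest.** Aim 2 is descriptive, names no summary statistic for the 5-minute target, and Aim 3 speaks of predictors and association. This also stands. But Hypothesis 2 still sets a threshold to be met, and an association with minutes on the ground is hard to interpret if it may only reflect who was in the room.

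**Conclusion.** The gap is real: both time variables are analysed over all falls, witness status is neither recorded nor adjusted for, and the wordings of discovery time disagree on what a witnessed fall receives.

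Its size is conditional. Under zero coding, the reported percentage within 5 minutes rises by w(1 − p), which is 5 to 20 points for p = 0.50 and w of 10–40%. In Aim 3, confounding requires transfer rates that differ by witness status. It then acts through discovery time if witnessed falls are coded near 0, and through ground time under zero or call-time coding. With equal transfer rates it vanishes.

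A reader might go further and conclude that Aim 3 will report a dose-response that does not exist. The documents do not support that, because the rejection rates above rest on assumed shares, transfer rates and time distributions. Aim 1 is untouched. This is a cheap improvement of minor to moderate severity.

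**What to change.** Before outcome data are examined:

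1. In the planned case review, add two fields coded from the video: staff in the room at the moment of the fall (yes or no), and fall versus intentional move to the floor. State whether intentional moves are excluded from the fall set.
2. Use one definition of discovery time in the Aims, Design and Clinical outcomes sections, including what is recorded when staff reach the resident before the call.
3. Assess the 5- and 15-minute targets on unwitnessed falls, and tabulate witnessed falls separately.
4. Fit the Aim 3 time model to unwitnessed falls, or keep all falls and add witness status as a covariate.

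The cost is two fields in an existing review and a few sentences, with no extra residents or procedures. The downside is fewer falls in the time analyses: at an assumed 20% witnessed share, 473 × 0.8 = 379 in one arm, or 947 × 0.8 = 757 over all residents. The result against the 5-minute target may also look less favourable.

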#### Participant recruitment and retention

In the Phase I project, recruitment was performed by hosting a family night with care staff from the facility. Recruitment rate among families attending family nights was 85%. Our retention over 10 months with the 11 partner facility was near 100% (no family / resident ever requested to remove the system). One resident did begin taking the sign off the door after enrolling in the study, and the system was removed with approval from the family since he may have been attempting to object to the study. We credit this high retention to the very little burden required.

The recruitment of 460 residents will happen in batches (we expect to have access to our entire cohort 6 months from the start of the project). Once the resident population is recruited, we will deploy the system and onboard the facility staff. Onboarding will be gradual over 3 months. Through randomization, the population is split in half. One half, the control group, will not receive the intervention for the first 6 months, but will get the intervention for the next 6 months. The other half, the intervention group, will be in the study for the first 6 months only and then continue for the next 6 months. In total, 12 months will be needed per cohort. Installing the system requires 1-5 days depending on the facility size to mount the SafelyYou Guardian in the electrical closet alongside the router and PoE switches required to connect and power the cameras. Installation will be provided by SafelyYou contractor.

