#### **Data collection:**

Demographic and clinical data set: We collect demographic data including age, gender, race/ethnicity, primary clinical diagnoses for SNF stay with specific focus on dementia subtype, most recent orthopedic surgery (<3 months) or reason for hospitalization, chronic medical conditions (top 3), and baseline medications (number of medications). Beyond the data collected from the video, data specific to the falls is collected either by direct extraction from the platform or from incident reports kept by facilities as (State regulations require facility track and file incident reports for all known falls). For the control population, the time of unwitnessed falls is unknown, but the number of falls and ER visits is collected from the existing facility incident reports. For the population equipped with SafelyYou Guardian, we will have direct access to the time of the fall, the time it took the HIL to verify the fall and call the facility, and the time on the ground. Note that for the residents with SafelyYou Guardian, we expect these values to be in increments of minutes.

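### The model linking discovery and ground time to ER visits and hospitalizations pools residents monitored at once with waitlist residents monitored 6 months later, with no stated covariate update at crossover, no group or period term, and no allowance for dropout before crossover

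*Combined protocol and SAP*

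**What the plan says.** - **Cohort.** Design, Aim 2: "We intend to include all 460 participants' data from Aim #1". These are the 230 residents monitored from the start and "the additional participants who are on the waitlist control group who will receive the intervention in the second 6month period". The waitlist residents are offered the extension; entry is not automatic.
- **Model.** The same Design paragraph asks whether the two times predict ER visits or hospitalizations. It adjusts for baseline characteristics, which it spells out as demographics and medical conditions, and for facility size. The Data analysis paragraph (under Clinical outcomes) gives the Aim 3 regression: the same two times as main predictors, with baseline participant and facility characteristics as controls. Neither place includes a term for randomized group or calendar period.
- **Covariates collected.** Data collection lists demographics, dementia subtype, chronic conditions, number of medications and "most recent orthopedic surgery (<3 months) or reason for hospitalization". It gives no date for this collection and states no repeat.
- **Later events.** For falls in both groups, Design (Aim 3) collects ED visits, hospital days, operations and other procedures, with biweekly checks in the control group. Clinical outcomes (Aim 3) adds comorbidities, ER visits and hospitalizations reported by legal representatives.
- **Follow-up.** Participant recruitment and retention says that the intervention group "will be in the study for the first 6 months only and then continue for the next 6 months". Clinical outcomes says: "Aim #2 will be a naturalistic observation of SafelyYou Guardian with HIL for 6 months".
- **Dropout.** Data analysis: "The dropout rate was roughly at ~1% per month so a 10% dropout over 6 months is a conservative estimate".

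**The concern.** Discovery time and ground time exist only for monitored falls, so the association model has to use this staggered cohort. Two features of the stagger are not handled.

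First, a waitlist resident's clinical state may have changed between enrolment and the start of monitoring. If the enrolment values are used, the adjustment is less accurate for that group than for the group monitored at once.

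Second, the two groups are monitored in different periods. Staff experience with the system may shorten response times, which are the predictor. The Purpose and Risk/Benefit sections say that seeing the video also affects whether a resident is sent to the emergency room, which is the outcome. A period difference that moves both could appear as an association between delay and ER use. A single time summary set against the 5- and 15-minute targets could also average over two unlike periods.

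The stated cohort size, and how much monitored time each group contributes, are also left unsettled.

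**Working it through.** **1. The plan's figure.** For Aim 2, 460 = 230 + 230, which is everyone randomized. It is the Aim 1 sample size carried over. As an approximate check of that size, I assumed two-sided alpha 0.05 (the plan states none) and read 0.467 as a standard deviation:

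- marginal rate 0.49 × exp(0.467²/2) = 0.546 falls per month
- per arm, one month: (1.96 + 0.842)² × (1/0.546 + 1/(0.7 × 0.546)) / (ln 0.7)² ≈ 274.2
- factor for six months at correlation 0.8: (1 + 5 × 0.8)/6 = 0.833
- 274.2 × 0.833 ≈ 228.5 per arm, 457 in total, close to 460

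Dividing by 0.9 for dropout would give 508. The plan's figure came from a simulation, so this does not settle how dropout entered it. However it was built, 460 is a number randomized, not a number still present at month 6.

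**2. Residents who start monitoring.** N = 230 + 230 × r × a, where r is retention to month 6 and a is acceptance of the extension. The plan gives r in two forms and does not give a.

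| r | Waitlist starting (a = 1) | Total | Short of 460 |
|---|---|---|---|
| 10% lost over 6 months: 0.90 | 207.0 | 437.0 | 23.0 (5.0%) |
| 1% lost per month: 0.99^6 = 0.9415 | 216.5 | 446.5 | 13.5 (2.9%) |

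The waitlist group is 207.0/437.0 = 47% to 216.5/446.5 = 48% of the pool. If acceptance were 85% (an assumption), the totals would be 405.9 and 414.1.

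**3. Age of the covariates at a monitored fall,** if recorded at enrolment and not updated, with monitoring starting on schedule:

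| Group | Range, months | Midpoint, months |
|---|---|---|
| Initial, monitored for 6 months | 0 to 6 | 3 |
| Initial, if monitored for 12 months | 0 to 12 | 6 |
| Waitlist | 6 to 12 | 9 |

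Only items that can change are affected: medical conditions and, if they enter the model, recent surgery, reason for hospitalization and medication count. Sex, race/ethnicity and facility size do not age, and age shifts by a known amount. A recent surgery recorded at enrolment is outside its 3-month window for every waitlist resident at month 6. For the initial group it passes out of the window by month 3.

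**4. Monitored time and load.** Ignoring dropout, if each group is monitored for 6 months they contribute equal time. If the initial group continues to month 12, it contributes 12/(12 + 6) = 67%. Monitored residents per facility start at 230/19 = 12.1. In months 7–12 the number depends on the same unresolved sentence:

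- initial group stops: 207/19 = 10.9 to 216.5/19 = 11.4
- initial group continues: (207 + 207)/19 = 21.8 to (216.5 + 216.5)/19 = 22.8

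So the load on staff either stays about level or nearly doubles.

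**The case against.** The case against is substantial.

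- **Later events are collected.** A reader might infer that surgery and hospital stays in the control period are lost. The documents do not support that. Design (Aim 3) and Clinical outcomes (Aim 3) provide for operations, comorbidities and hospitalizations. The first source is tied to falls, so capture may be incomplete, and neither is said to update the covariates.
- **Recent surgery may not be in the model.** Design names only demographics and medical conditions. Data collection lists what is recorded, not what is adjusted for. This stands, so the surgery window is an illustration and not the core of the point.
- **Baselines age in the initial group too.** This stands. The difference is one of degree: a midpoint of 3 months against 9, or 6 against 9 if the initial group continues.
- **The baseline date is inferred.** This stands. It rests on the Aim 1 comparison of baseline characteristics between arms. Re-collection is unstated, not excluded.
- **The size and direction of any bias are unknown.** This stands. Nothing in the documents shows that health status at the fall is the main confounder, or by how much staff experience changes response times.
- **The count hardly matters.** Aim 2 is descriptive, has no sample-size target and measures times per fall. Including all 460 is worded as an intention. This largely stands: the figure is worth correcting but is not a failure of the design.

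The Data analysis paragraph also does not say who enters the Aim 3 regression. But its main predictors exist only for monitored falls, so the pooled cohort of Design is the natural reading. The intervention-versus-control comparison in Hypothesis 3 is not affected.

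**Conclusion.** The point holds in a limited form, as a low-cost improvement to a secondary, observational analysis. The plan pools two groups monitored 6 months apart. It does not say whether changeable covariates are updated at crossover, and it has no group or period term. If baseline is taken at enrolment, those covariates are at least 6 months old when monitoring begins for 47% to 48% of the pool. The resulting bias cannot be quantified from the documents.

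On the plan's own dropout, about 437 to 446 residents would start monitoring, a shortfall of 3% to 5% before declined offers. It would go too far to say that the Aim 2 analysis fails for want of numbers, or that all covariates are invalid for half the cohort. Aim 1 power is unchanged.

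The statement on the intervention group's follow-up in Participant recruitment and retention is internally inconsistent. Until it is reconciled, each group's share of monitored time, and the load on staff in months 7–12, are undefined.

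**What to change.** 1. When each waitlist resident starts monitoring, update the Data collection items that can change, using the event data already planned under Aim 3 where available. State that these values enter the Aim 2/3 association model.
2. Add a group or period term to that model, and show the discovery-time and ground-time summaries separately for the initial and waitlist groups.
3. Restate the expected Aim 2 number as about 437 to 446 before declined offers.
4. Reconcile the follow-up sentence in Participant recruitment and retention with Design and Clinical outcomes, so that each group's monitored time is defined.

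The cost is a short chart update for about 207 to 217 residents, one more model term, a few sentences of plan text and a slightly lower stated number. The update is best done at crossover, because the information is harder to recover afterwards.
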